4.5.1.3 Postponement of cures, modification of administration and reason

- The number and percentage of patients with at least one deferral of treatment and the reasons for these deferrals
- The number of patients who had at least one dose change will be described. The causes of dose modifications will be presented. A listing of others will be provided.
- The number and percentage of patients who have permanently stopped the protocol treatment and the reasons for stopping treatment will be described.

All parameters will be described according to standard descriptive statistics.

4.5.1.4 Subsequent lines

- The number of patients who received a subsequent line and subsequent patterns will be described.
- The number of patients who had resection of the primary and metastases and the outcome of the resection will be described.

All parameters will be described according to standard descriptive statistics.

4.5.2 Toxicities

On-treatment toxicities will be described according to NCI-CTC version 4.0 criteria by:

- The number and percentage of patients who experienced at least one toxicity over all courses of treatment by grade;
- The number and percentage of patients who experienced at least one maximum grade 3-4-5 toxicity over all courses or at least one maximum grade 1-2 toxicity;
- Toxicities will be described according to causality to treatment and by SOC (by preferred term).
- The number of toxicities that resulted in an SAE

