## EXAMINATION AND FOLLOW-UP SCHEDULE

	Before inclusion			During treatment (until progression)					After treatment
	J -21	J -14	J -7	C1 : D1, D7 and D14 C2 : D1, D7 and D14	D1 of each cycle (every 4 weeks)	D14 of each cycle	Every 8 weeks after the start of treatment	End of treatment visit	Every 8 weeks
Informed consent	X								
Clinical examination		X		X	X		X	X	X
Weight, height, BP		X		X	X		X	X	
ECOG		X			X		X	X	X
Geriatric questionnaires, quality of life		X			X		X		
Biological check-up 1 			X		X		X		
Biological check-up 2 						X		X	
Urine dipstick ± 24h proteinuria		X			X		X		
ECG		X			X 				
Thoracic and abdominal-pelvic CT	X						X		
ACE			X		X		X		
Cardiac ultrasound or myocardial scintigraphy ± cardiological opinion in case of cardiopathy 	X								
Assessment of treatment toxicity				X	X		X	X	

Biological check-up 1: CBC-PQ, natraemia, kalemia, calcemia, magnesemia, phosphoremia, uricemia, creatininemia, albuminemia, ASAT, ALAT, PAL, total and conjugated bilirubinemia, GGT, TP, TSH, lipase, INR for patients treated with AVK.

Biological check-up 2: CBC-Pq, natraemia, kalemia, creatinine, creatinine clearance, ASAT, ALAT, PAL, total and conjugated bilirubin, GGT INR for patients treated with AVK.

 For patients treated with an anti-coagulant, a coagulation test should be performed, if the values are outside the therapeutic range the dose of anticoagulant should be modified and a coagulation check should be done every week until stabilization.

 During treatment, an ECG will be done according to the investigator's choice.

 In case of heart disease, cardiac echography or myocardial scintigraphy, completed by a cardiologist's opinion if necessary, **dated less than 3 months before inclusion.**

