## 3. PATIENT SELECTION

### 3.1 Inclusion criteria

- Metastatic colorectal cancer with histological evidence
- Measurable disease according to RECIST 1.1 criteria
- Age  $\geq$  70 years
- ECOG  $\leq$  1
- Life expectancy greater than or equal to 3 months
- Biological workup: hemoglobin  $\geq$  9 g/dL, PNN  $\geq$  1500/mm^3, platelets  $\geq$  100,000/mm^3, bilirubin  $\leq$  1.5N, AST, ALT and PAL  $\leq$  2.5N ( $\leq$  5N if liver metastases), lipase  $\leq$  1.5N, PT  $\geq$  70%, creatinine clearance  $\geq$  30 mL/min
- Patients who have failed fluoropyrimidine-based chemotherapy, anti-VEGF therapy, and anti-EGFR therapy (if the cancer expresses the non-mutated RAS gene), who have progressed on this therapy, or patients who have discontinued this therapy for unacceptable toxicity
- Completed geriatric patient and team questionnaires
- Signed informed consent

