### 3.2 Criteria for non-inclusion

- Inability to swallow tablets (crushed tablets are not allowed)
- **Previous treatment with regorafenib or another multikinase inhibitor**
- Other cancer within 5 years prior to inclusion, except cervical cancer *in situ*, non-melanoma skin cancer and superficial bladder cancer treated curatively
- Radiation therapy: - with extended fields, within 4 weeks, - with limited fields, within 2 weeks, prior to inclusion. The site treated in this way must have demonstrated progression, if it is the only evaluable site
- Unresolved  $>$  grade 1 toxicity attributed to prior therapy
- Major surgery within 28 days of starting treatment
- Unhealed wound, ulcer or bone fracture
- Congestive heart failure of class  $>2$  according to the NYHA classification
- Unstable angina or angina that started less than 3 months ago
- Myocardial infarction less than 6 months before the start of treatment
- Uncontrolled hypertension (systolic pressure  $>$  150 mm Hg or diastolic pressure  $>$  90 mm Hg despite optimal treatment)
- Pheochromocytoma
- Arterial or venous thromboembolic event within 6 months prior to the start of treatment
- Clinically active infection of grade  $>2$
- HIV infection
- Chronic viral hepatitis B or C requiring antiviral treatment
- Cirrhosis
- Known or suspected brain metastasis
- Bleeding grade  $>3$  within 4 weeks of starting treatment
- Symptomatic pulmonary fibrosis
- Proteinuria  $>$  grade 3
- Malabsorption
- Known hypersensitivity to the study drug or to a drug of the same class or to an excipient
- Systemic anti-cancer treatment during the study or within 4 weeks prior to initiation of treatment
- Concomitant treatment with a CYP3A4 inhibitor or inducer or a UGT1A9 inhibitor
- Social, psychological or medical condition that may interfere with participation in the study or its evaluation

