Elevated ALT and/or AST levels	Occurrence	Dosage changes and recommended actions
$\leq$ 5 times the upper limit of normal (ULN) (Grade 2 maximum)	All cases	Continue regorafenib therapy. Monitor liver function weekly until transaminases return to $<$ 3 times ULN (grade 1) or to baseline.
$>$ 5 times ULN (Grade 3) $\leq$ 20 times ULN	1 re occurred	Discontinue regorafenib. Monitor transaminases weekly until they return to $<$ 3 times ULN or to baseline. Resumption of treatment: reinstate regorafenib, reduce dose by 40 mg (one tablet) if potential benefit outweighs risk of hepatotoxicity. Monitor liver function weekly for at least 4 weeks.
	New occurrence	Permanent discontinuation of regorafenib.
$>$ 20 times ULN (Grade 4)	All cases	Permanent discontinuation of regorafenib.

Elevated ALT and/or AST levels	Occurrence	Dosage changes and recommended actions
> 3 times ULN (Grade 2 or higher) with concomitant elevation of bilirubin > 2 times ULN	All cases	Permanent discontinuation of regorafenib. Monitor liver function weekly until normalization or return to baseline. Exception: Patients with Gilbert's syndrome who develop elevated transaminases should be managed as described above for corresponding elevations in ALT and/or AST.

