## **11.3 Calculation of the number of subjects required**

The clinical assumptions are based on data from the CORRECT study and are as follows:

$H_0$  : A tumor control rate at 2 months after the start of treatment of 25% or less is not sufficient

$H_1$  : A tumor control rate at 2 months after the start of treatment of more than 25% is considered sufficient. A rate of 47% is expected.

With a one-sided  $\alpha$  risk of 5% and 90% power, 42 patients are required.

Patients who discontinue the study prior to documented tumor progression at 2 months will be considered non-responders for the primary endpoint analysis.

The decision rules after inclusion of 42 patients are:

If 15 or fewer patients show a complete or partial response or stability, then the treatment will be considered not effective.

If 16 or more patients have a complete, partial or stable response, then the treatment is considered effective.

A recruitment of 2 patients per month is planned.

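### The toxicity tables have no new-or-worsened rule and ignore the SAP's own baseline, so unchanged entry abnormalities can be counted, mainly in the grade 1-2 rows

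*SAP*

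**What the plan says.** **Toxicity tables.** SAP 4.5.2 covers on-treatment toxicities, a term it does not define. Its first item is "The number and percentage of patients who experienced at least one toxicity over all courses of treatment by grade". Its second groups patients by worst grade, 3-4-5 or 1-2. A third item breaks toxicities down by causality and by organ class and preferred term. Protocol 11.4 (Tolerance analysis) plans counts by grade and organ class, with no causality split.

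**Baseline.** SAP 3.4 defines baseline as the last measurement before inclusion or before the first administration. SAP 4.5.2 does not refer to it.

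**What patients may bring with them.**
- Protocol 3.1 raises the AST, ALT and PAL limit to "5N if liver metastases".
- Table B of Protocol 7.2 labels ALT/AST values up to 5 "times the upper limit of normal (ULN) (Grade 2 maximum".
- Protocol 3.2 excludes unresolved toxicity only above "grade 1 toxicity attributed to prior therapy".

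**When toxicity is collected.** In the examination schedule, the row "Assessment of treatment toxicity" has no entry before inclusion and starts at cycle 1 day 1. Protocol 7.2 has clinical assessment on days 1, 7 and 14 of cycles 1 and 2, and laboratory grading on days 14 and 28. Protocol 8.1 lets a recent inclusion blood test serve as the cycle 1 day 1 test.

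**The concern.** A count of grades reached during treatment measures what happened on the drug only if findings already there are set aside. Here they need not be. A patient with liver metastases and a stable grade 2 transaminase has a gradable value at day 14 although nothing has changed. A grade 1 symptom left over from earlier chemotherapy can be noted on the day of the first tablet.

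Tolerance in elderly patients is a stated secondary objective, and the study has a single arm, so no control group shows the background rate. Comparison with the patient's own entry grade is the main objective safeguard. The SAP defines the baseline for that comparison but does not apply it here. A reader of the term-level tables could take part of the burden of advanced disease or earlier therapy for an effect of treatment.

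**Working it through.** **1. The plan's only design figure, and why it is not involved.** Protocol 11.3 states a one-sided "risk of 5% and 90% power, 42 patients are required", with success at 16 or more. The exact binomial gives P(X ≥ 16 | n = 42, p = 0.25) = 0.0416 and P(X ≥ 16 | n = 42, p = 0.47) = 0.9057. The figure is reproduced. The present point does not touch the primary endpoint and uses 42 only as a denominator.

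**2. Is there a rule elsewhere?** The adverse event definition in Protocol 10.2 has no onset or worsening condition, and all events are recorded by grade. Protocol 11.4 adds none. SAP 3.4 supplies a baseline but no rule for using it with toxicity. The rule is missing from both documents.

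**3. By which route can an entry finding be counted?**
- Transaminases: admitted up to 5N, grade 2 at most, graded again at day 14. They enter by persisting to day 14, not through the cycle 1 day 1 sample.
- Residual symptoms: admitted at grade 1, collected clinically at cycle 1 day 1.
- Both are grade 1-2. On the documents' own grades neither can add a patient to the 3-4-5 group.
- Possible exceptions: proteinuria is excluded only above grade 3 as worded, and GGT is measured but has no entry limit. The documents give nothing from which to size either.

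**4. Size in a grouped liver-test row (assumptions, not document figures).** Suppose 40-70% of patients have liver metastases and 30-50% of those enter with an abnormal AST, ALT or PAL.
- Low: 0.40 × 0.30 = 12%; 0.12 × 42 = 5.0 patients.
- High: 0.70 × 0.50 = 35%; 0.35 × 42 = 14.7 patients.

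This is an upper bound. It takes every abnormality to persist and to be recorded as a toxicity, and it pools three tests, so a single preferred term would show less.

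Some of these patients would worsen anyway. With entry share b and true incidence t of new or worsened events, taken as independent of b, the reported share is b + (1 − b)t and the excess is b(1 − t). For an assumed t of 20-40%:
- Smallest: 0.12 × 0.60 = 7.2 points, 3.0 patients.
- Largest: 0.35 × 0.80 = 28 points, 11.8 patients.

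**5. Size in the overall patient counts.** Protocol 1.2 reports treatment-related effects in 91.7% of patients aged 65 or over in the earlier phase III study. If that applies here, at most 8.3% × 42 = 3.5 patients have no toxicity to report. Taking 12-35% of them, again assuming independence, gives 0.4 to 1.2 extra patients in the overall any-grade count. The same section gives related grade 3 or higher rates of 57% (65-74 years) and 66% (over 75). An entry finding of grade 1-2 cannot change the worst grade of those patients.

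**The case against.** The strongest reply is that the SAP is silent rather than wrong. It restricts the tables to on-treatment toxicities, a term that could be read to exclude pre-dose findings. A reader might infer that the SAP orders every recorded grade to be counted; no section says so. Whether a stable laboratory value becomes a toxicity record at all depends on the observation booklet, which is not in the text. This stands, and it is why the counts can include entry findings rather than certainly do. It does not remove the gap, because the term is undefined and two analysts could program it differently.

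A reader might also infer that everything in the tables is presented as caused by regorafenib. The documents do not support that: SAP 4.5.2 has a causality breakdown, and Protocol 10.2 offers unrelated and doubtful categories. But the first two items of SAP 4.5.2 and the organ-class counts of Protocol 11.4 have no causality filter. Causality is also an investigator's judgement in an open-label study, and it is hard to make for liver tests in patients with liver metastases.

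Finally, the analysis is descriptive and secondary, and the overall counts hardly move. That is correct and limits the importance of the point.

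**Conclusion.** The point holds in limited form. As written, the all-cause toxicity counts can include unchanged abnormalities from before treatment, chiefly in the grade 1-2 rows for individual terms or organ classes. The overall any-grade count would change by about one patient or less on the rates quoted in Protocol 1.2, and the grade 3-5 counts little, with proteinuria and GGT as possible exceptions of unknown size. The primary endpoint and its decision rule are unaffected.

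The true size cannot be computed from the documents. The 5 to 15 of 42 for a grouped liver row rests on assumed shares of liver metastases and abnormal entry tests and is a ceiling, not an estimate. Haemoglobin and other entry limits were left out because the grading table is not in the text. This is an inexpensive improvement to a descriptive analysis, worth making because there is no control arm.

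**What to change.** In SAP 4.5.2:
- Define the baseline grade as the last grade before the first tablet, from the inclusion work-up or the pre-dose cycle 1 day 1 assessment, in line with SAP 3.4.
- Count as on-treatment toxicity only events that are new, or of higher grade than baseline, after the first tablet. Apply this to the by-grade, grouped-grade and organ-class tables.
- Add a table of baseline grade by worst on-treatment grade for laboratory items.
- Keep the causality table.

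SAP 1.6 requires changes before the database is frozen. The cost is a paragraph of text and a little programming, since the inclusion laboratory values and the day 1 assessment are already collected. There are two downsides. Reported grade 1-2 rates will fall. Clinical findings at cycle 1 day 1 must be identifiable as pre-dose; no graded toxicity assessment is scheduled earlier, so if the booklet does not separate them, a data query or a stated convention is needed.

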4.5.3 SAEs

A summary of the SAEs will be provided by pharmacovigilance.

4.6 Exploratory analyses

4.6.1 Definition

The exploratory analysis will investigate the predictive factors for response, overall survival, and progression-free survival with regorafenib therapy.

Prior to any inferential analysis, descriptive statistics of the predictive factors will be performed to assess the feasibility of this analysis.

The variables for which the p-value is lower than 0.20 in univariate analysis or judged clinically relevant among the list to be defined will be retained for the multivariate analysis. The prognostic factors studied will be the geriatric parameters.

4.6.2 Evaluation

For univariate and multivariate analyses, hazard ratios will be estimated using a Cox model (Cox, 1984). The proportionality of the rates will be tested using the graphical representation and the test based on Schönfeld's residuals (Grambsch, 1994); the linearity of the effect of the continuous variables on the risk will be assessed from the graphical representation of the martingale residuals. Confidence intervals for the coefficient estimates of the Cox models will be calculated using the Wald method.

Several multivariate models can be constructed. The comparison of the different models obtained will be carried out according to a measure of adequacy of the model (AIC), a measure of calibration (O'Quigley's R^2) and a measure of accuracy (Breier score).

In an exploratory way, in order to study the temporal evolution of geriatric and quality of life scores (Spitzer QoL Index, IADL, ...), mixed models of analysis of variance for repeated measures of each of the scores will be carried out.
